Study I5Q-JE-CGAP (Study CGAP) is a multisite, randomized, long-term (1-year), two arms, open-label study. This study will be evaluating the safety and effectiveness of galcanezumab (120 mg/month and 240 mg/month) in the prevention of migraine headache. As shown in protocol I5Q-JE-CGAP (protocol CGAP), Japanese patients with episodic migraine (EM) will roll over from Study I5Q-JE-CGAN. In addition to these patients with EM, Japanese patients with chronic migraine (CM) will be also enrolled in the study CGAP. The objective of this addendum is to evaluate safety and effectiveness of galcanezumab in Japanese patients with CM. Schedule of Activities, Objective and Endpoints, Study Design, Study Population, Treatments, and Statistical Consideration are described in this protocol addendum (1).

4. Protocol Additions

The content below will apply to patients with CM enrolled in Study CGAP. The rest of the parts of the protocol should be referred to the main protocol.

2. Schedule of Activities

This is for the patients with CM.

Study Period (SP)	SP I- Screening	SP II- Prospective Baseline	SP	III – 7	Гrea	tmer	ıt										SP I Follo up	
(Target) Interval (days) since previous visit			30- 45	14	16	30	30	30	30	30	30	30	30	30	30	30	60	60
Allowable range (days) between visits	3-45	30-40a																
Interval allowance (days) compared from previous visit				±3	±3	±7	±7	±7	±7	±7	±7	±7	±7	±7	±7	±7	±7	±7
Visit	1	2	3ª	4	5	6	7	8	9	10	11	12	13	14	15	16/ ET	17	18/ ET
Month			0	(D14)	1	2	3	4	5	6	7	8	9	10	11	12	14	16
Assessments and	Procedures	S																
Informed consent	X																	
Inclusion/Exclusi on	X	X	X															
Demographics	X																	
Physical examination ^b	X																	
Height	X																	
Weight	X									X						X		X
Waist and hip circumference	X																	
Medical history	X																	
Pre-specified migraine history/ pre-therapy		X																
Substance use	X																	
Prior Therapy (Migraine Medication)	X																	
ECG ^c	X		X							X						X		X
Vital signs ^d	X		X		X	X	X	X	X	X			X			X	X	X
Adverse events	X	X	X	X	X	X	X	X	X	X	X	X	X	X	X	X	X	X

Study Period (SP)	SP I- Screening	SP II- Prospective Baseline	SP	SP III – Treatment							SP IV – Follow- up							
(Target) Interval (days) since previous visit			30- 45	14	16	30	30	30	30	30	30	30	30	30	30	30	60	60
Allowable range (days) between visits	3-45	30-40a																

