Abbreviations: CGRP = Calcitonin-gene related peptide; CRP = Lilly Clinical Research Physician; CRS = Lilly Clinical Research Scientist; C-SSRS = Columbia Suicide Severity Rating Scale; D14 = Day 14; DNA = deoxyribonucleic acid; ECG = electrocardiogram; ET = early termination; FSH = follicle stimulating hormone; HbA1c = glycated haemoglobin; HCRU = Health Care Resource Utilization; MIDAS = Migraine Disability Assessment test; MSQ (v2.1) = Migraine Specific Quality of Life Questionnaire; PGI-I = Patient Global Impression of Improvement; PGI-S = Patient Global Impression of Severity; PK = pharmacokinetics; PSMQ-M = Participant Satisfaction with Medication Questionnaire-Modified; RNA = ribonucleic acid; SP = Study Period; SHSF = Self-harm supplement form; SHFU = Self-harm follow-up form.

Note: Selected tests may be obtained in the event of a treatment-emergent hepatic abnormality and follow-up may be required with patients in consultation with the Lilly, or its designee (CRP/CRS). See Appendix 4 of the protocol for more details regarding specific hepatic monitoring tests. If the patient has discontinued the trial and returns for hepatic follow-up, the site should use the 800 series as the visit designation.

- ^a The eligibility period of the prospective baseline assessment will last from 30 to 40 days. Investigators and patients may have up to an additional 5 days to schedule their Visit 3 appointment (beyond the 40 days); however, eligibility will be based on the 30-40 day period.
- b Physical examinations at screening must include a neurological exam.
- ^c Electrocardiograms as single, 12-lead digital will be performed at Visit 1, Visit 3, Visit 10, Visit 16, and Visit 18 or early termination. Note: The Visit 3 ECG should be collected prior to blood draws and dosing. Patients must be supine for approximately 5 to 10 minutes before ECG collection and remain supine but awake during ECG collection. For screening only, ECG results will be read locally.
- Vital signs will include body temperature, blood pressure, and pulse. Blood pressure and pulse will be measured in triplicate in the sitting position and should be measured prior to blood draws. Blood pressure will be assessed by utilizing a calibrated machine.

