5.1. Overall Design

Figure CGAP(1).1 illustrates the study design for CM patients.

Abbreviation: SP = study period.

Note: The Visit 3 injections are under blind condition for all patients. From Visit 5, patients receive either one 120 mg injection (120 mg arm) or two 120 mg injections (240 mg arm) without blinding

Figure CGAP(1).1. Study design for patients with chronic migraine.

Study Period I (SPI): The study and potential risks will be explained to the patient at Visit 1. The informed consent form (ICF) must be signed before any study procedures are performed.

Patients are required to discontinue all excluded medications or treatments for migraine prevention at least 30 days prior to Visit 2. Botulinum toxin A or B in the head or neck area must be discontinued at least 4 months prior to Visit 2.

The screening visit (Visit 1) will consist of a full clinical assessment, including a comprehensive medical evaluation documenting medical history, and a physical and neurological examination. Visit 1 will be complete when the last scheduled procedure of the screening assessment for the patient is completed.

Study Period II (SPII): Qualified patients will enter Study Period II (prospective baseline) to determine their eligibility for the study and to establish baseline data for comparison of endpoints during open-label treatment period. Patients will be trained to keep track of their migraine and headache days as well as their medication use days using a paper-based headache diary (paper diary) by the site staff. Retraining will be conducted as necessary based upon review of paper-diary data.

To avoid biased reporting, patients must not be told the number of headache days or migraine headache days on which study qualification is based.

Study Period III (SPIII): At Visit3, patients meeting all eligibility requirements will be randomized to receive galcanezumab 120 mg/month, or galcanezumab 240 mg/month in a 1:1 ratio.

^{*}Eligibility period determined between a minimum of 30 days and a maximum of 40 days. Investigators may have up to 5 additional days (beyond the 40 days) if needed to schedule patients' Visit 3 appointment.

^aPatients randomized to the 120 mg dose will receive a loading dose of 240 mg at the first injection only (Visit 3).

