10.3. Statistical Analyses

10.3.1. General Statistical Considerations

Unless specified otherwise, data for the patients with CM in Study CGAP will be reported by the following treatment groups;

- 1) CM120: CM patients who are randomized to galcanezumab 120 mg in Study CGAP
- 2) CM240: CM patients who are randomized to galcanezumab 240 mg in Study CGAP

Unless otherwise specified, safety and effectiveness analyses will be conducted on an intent-to-treat (ITT) basis, which is to include all patients who receive at least one dose of study drug. When change from baseline is assessed, the patient will be included in the analysis only if he/she has a baseline and a post-baseline measurement. In principle, any statistical analysis will be performed in a descriptive manner due to limited sample size and open-label treatment.

For analysis for the patient with CM, baseline is Visit 3 assessment in Study CGAP unless otherwise specified.

Details will be described in the statistical analysis plan (SAP) document.

Leo Document ID = 0ccc690c-0f9f-4806-9a1c-e4139d2a9c50

Approver: PPD

Approval Date & Time: 02-Sep-2016 15:21:28 GMT Signature meaning: Approved

Approver: PPD

Approval Date & Time: 02-Sep-2016 15:45:03 GMT Signature meaning: Approved

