Treatment emergent changes in vital signs, weight, and ECGs	Safety Population with a baseline and at least 1 post-baseline observation	EM: Visit 3 CM: Low: Minimum value from Visits 1–3 High: Maximum value from Visits 1–3	Low: Minimum value from Visits 3.01–16 High: Maximum value from Visits 3.01–16
Continuous safety analyses	Safety Population with a baseline and at least 1 post-baseline observation	EM: Visit 3 CM: Last of Visits 1–3	Scheduled visits: 3 < Visits ≤ 16
Study Period III and IV combined			
Efficacy analyses	ITT Population with a baseline and at least 1 post-baseline observation	Visit 3	All Visits 3.01-18
Quality of Life analyses	ITT Population with a baseline and at least 1 post-baseline observation	Visit 3	All Visits 3.01-18

Study Period/Analysis	Patient Population	Baseline Observation	Post-baseline Observation(s)
Continuous safety analyses	Safety Population with a baseline and at least 1 post-baseline observation	EM: Visit 3 CM: Last of Visit 1- 3	All Visits 3.01-18
Treatment emergent immunogenicity	ADA follow-up cohort (See Section 5.5.12.1.6)	EM (LY120/LY120, LY240/LY240): CGAN Visit 3 EM (PLA/LY120, PLA/LY240): CGAP Visit 3 CM: Visit 3	All Visits 3.01–18
Study Period IV			
Continuous safety analyses – change from baseline to LOCF endpoint (ANCOVA)	Post-treatment Population with a baseline and at least one post-baseline observation	EM: Last of Visits 3-16 CM: Last of Visits 1-16	Last Visit: 16.01-18
FEAEs	Post-treatment Population	EM: All Visits in CGAN Visit 1 - 16. CM: All Visits 1- 16. Pre-existing condition that is still ongoing at Visit 1 should be evaluated as baseline values.	All Visits 16.01–18
Serious Adverse Events, Discontinuations due to Adverse Events	Post-treatment Population	NA	All Visits 16.01–18
Follow-up emergent abnormal laboratory values	Post-treatment Population with normal laboratory values at all nonmissing baseline visits (with respect to direction being analyzed) and who have at least 1 post-baseline observation	EM: All Visits 3- 16 CM: All Visits 1- 16	All Visits 16.01–18
Follow-up emergent changes in vital signs, weight and ECGs	Post-treatment Population with a baseline and at least 1 post-baseline observation	EM: Low: Minimum value from Visits 3–16 High: Maximum value	Low: Minimum value from Visits 16.01–18 High: Maximum value from Visits 16.01–18

Study Period/Analysis	Patient Population	Baseline Observation	Post-baseline Observation(s)

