5.5.12.1.3. Vital Signs and Weight

Vital signs collected during the study include systolic and diastolic blood pressure, pulse, and temperature. Blood pressure and pulse will be measured in triplicate, in the sitting position, and

should be measured prior to blood draws. The 3 sitting blood pressure measurements and 3 pulse values will be averaged and used as the value for that visit. If the measurements are less than three, the averaged values on the available data will be used.

The number and percent of patients meeting criteria for treatment-emergent abnormalities in vital signs and weight at any time during study will be summarized (SP III and SP IV separately). Treatment group comparisons will be performed using the Fisher's exact test for SP III. [Table CGAP. 5.6](#) displays the criteria used to define treatment emergent changes in vital signs and weight. The last column of the table displays the patient populations defined by baseline categories, the treatment emergent categorical changes will be analyzed for each of those patient populations for SP III. The criteria generally consist of 2 parts, an absolute threshold and a change from baseline amount. The baseline and post-baseline definitions for vital signs analyses are in [Table CGAP. 5.4](#).

Table CGAP. 5.6 Criteria for Treatment-Emergent Categorical Changes in Vital Signs

Parameter	Direction	Criteria	Patients Population defined by Baseline Categories
Systolic BP (mm Hg) (sitting)	Low	≤90 and decrease ≥20	All patients; >90; ≤90
	High	≥140 and increase ≥20	All patients; <140; ≥140
	PCS High	≥180 and increase ≥20	All Patients; <180; ≥180
	Sustained Elevation	≥140 and increase ≥20 at 2 consecutive visits	All patients; <140; ≥140
Diastolic BP (mm Hg) (sitting)	Low	≤50 and decrease ≥10	All patients; >50; ≤50
	High	≥90 and increase ≥10	All patients; <90; ≥90
	PCS High	≥105 and increase ≥15	All Patients; <105; ≥105
	Sustained Elevation	≥90 and increase ≥10 at 2 consecutive visits	All patients; <90; ≥90
Systolic BP or Diastolic BP (mm Hg) (sitting)	Sustained Elevation	Meeting criteria for systolic BP for 2 consecutive visits or meeting criteria for diastolic BP for 2 consecutive visits or both	All Patients
Pulse (bpm) (sitting)	Low	<50 and decrease ≥15	All patients; ≥50; <50
	High	>100 and increase ≥15	All patients; ≤100; >100
	Sustained Elevation	>100 and increase ≥15 at 2 consecutive visits	All patients; ≤100; >100
Weight (kg)	Low	(Loss) decrease ≥7%	All patients

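### CM patients are not weighed at Visit 3, so their weight baseline is the screening value, 33 to 90 days before the first dose, and weight change before treatment counts as change on treatment

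*SAP*

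**What the plan says.** Weight is listed with vital signs among the endpoints of the primary safety objective (SAP Table CGAP. 4.1). It is analysed by ANCOVA to the LOCF endpoint in Study Period III, by MMRM over Study Periods III and IV combined (SAP 5.5.12.2), and as a categorical treatment-emergent change (SAP 5.5.12.1.3). The weight rows of Table CGAP. 5.6 rest on relative change alone: the low row reads "Loss) decrease ≥7" per cent, the high row mirrors it, and neither has an absolute threshold.

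Table CGAP. 5.4 gives the baseline for continuous safety analyses as "EM: Visit 3 CM: Last of Visits 1–3". For categorical changes in CM patients it uses the minimum (low direction) or maximum (high direction) over Visits 1 to 3. SAP 5.5.4 takes body weight for the baseline table from the last observation before the Visit 3 injection.

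The CM Schedule of Activities (protocol addendum, Section 2) marks weight at Visits 1, 10, 16 and 18 only. The Visit 3 vital signs do not supply it: "Vital signs will include body temperature, blood pressure, and pulse". The spacing of the early visits is given by "Allowable range (days) between visits 3-45 30-40a", and a footnote adds that "Investigators and patients may have up to an additional 5 days to schedule their Visit 3 appointment (beyond the 40 days". On earlier medication, addendum Section 5.1 says: "Patients are required to discontinue all excluded medications or treatments for migraine prevention at least 30 days prior to Visit 2".

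**The concern.** Blood pressure, pulse, temperature, ECG, haematology and chemistry are all taken at Visit 3, so the SAP's baseline rules reach the day of first dosing for those measures. For weight the same rules find only one scheduled value, at screening. Any gain or loss between screening and the first injection is then reported as change on treatment.

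The CM part of the study has no untreated arm. The absolute CM results are the safety finding, and nothing in the design subtracts the pre-dose drift. The 7% criterion depends only on the baseline, so a shift in the baseline passes straight into it. The SAP's weight analyses do not tell the reader that the CM reference point is a screening value, although the EM arms shown beside it in the four-arm safety tables are referenced to Visit 3.

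**Working it through.** **1. Is the schedule read correctly?** The tables were extracted from PDF, so the column positions need a check. Counting columns the same way places the ECG row at Visits 1, 3, 10, 16 and 18. The ECG footnote gives the same visits: "Electrocardiograms as single, 12-lead digital will be performed at Visit 1, Visit 3, Visit 10, Visit 16, and Visit 18 or early termination". The same count places weight at Visits 1, 10, 16 and 18, so the empty Visit 3 cell is real.

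**2. What the baseline rules return for CM weight.** With one scheduled pre-dose value W1, the last of Visits 1–3, the minimum of Visits 1–3 and the maximum of Visits 1–3 all equal W1.

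**3. Age of that value at first dose.**
- Visit 2 to Visit 3: shortest 30 days, longest 40 + 5 = 45 days. This reproduces the schedule's own target interval of 30–45 days.
- Visit 1 to Visit 2: 3–45 days.
- Visit 1 to Visit 3: 3 + 30 = 33 days to 45 + 45 = 90 days.

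**4. Position relative to stopping preventives.** The latest permitted stop is 30 days before Visit 2. Let g be the Visit 1 to Visit 2 interval.
- g = 3–29 days: the drug must have stopped at least 30 − g = 27 to 1 days before Visit 1.
- g = 30–45 days: stopping can fall on or after Visit 1, by at most 45 − 30 = 15 days. In these patients the Visit 1 to Visit 3 gap is 30 + 30 = 60 to 90 days.
- Botulinum toxin must stop at least 4 months before Visit 2, so always before Visit 1.

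**5. Share of the measured interval that lies before dosing.** With d the Visit 1 to Visit 3 gap, nominal time from first dose is 14 + 16 + 5 × 30 = 180 days at Visit 10 (Month 6) and 180 + 6 × 30 = 360 days at Visit 16 (Month 12).
- Month 6, d/(d + 180): 33/213 = 15.5%; 90/270 = 33.3%.
- Month 12, d/(d + 360): 33/393 = 8.4%; 90/450 = 20.0%.

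**6. Effect on the mean change.** W_post − W1 = (W_post − W3) + (W3 − W1). The raw mean change shifts one for one by the mean Visit 1 to Visit 3 drift. Covariate adjustment does not remove the shift, because the baseline covariate is W1 itself.

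**7. Effect on the 7% rates: illustration on assumed inputs.** The documents give no weight SD and no drift. Assume one post-baseline value, no true effect, on-treatment percentage change with mean 0 and SD s, and an independent pre-dose percentage drift with mean m and SD p, all normal.
- Visit 3 baseline, gain or loss: 1 − Φ(7/s).
- Visit 1 baseline, gain: 1 − Φ((7 − m)/√(s² + p²)); loss: Φ((−7 − m)/√(s² + p²)).

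| s | m | p | Visit 3 baseline, gain or loss | Visit 1 baseline, gain | Visit 1 baseline, loss |
|---|---|---|---|---|---|
| 3 | 0 | 1 | 1.0% | 1.3% | 1.3% |
| 4 | 0 | 2 | 4.0% | 5.9% | 5.9% |
| 4 | 1 | 2 | 4.0% | 9.0% | 3.7% |
| 5 | 2 | 2 | 8.1% | 17.7% | 4.7% |

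Over s = 3–5, m = 0–2 and p = 1–2, a gain of 7% or more runs from 1.0% to 8.1% with a Visit 3 baseline and from 1.3% to 17.7% with a Visit 1 baseline. A loss of 7% or more runs from 1.0% to 8.1% and from 0.2% to 9.7%. A downward drift mirrors gain and loss. In an arm of 30, the third row's rise in gain from 4.0% to 9.0% is 0.05 × 30 = 1.5 patients.

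**The case against.** Much can be said for the plan, and several stronger readings fail.

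- **Conflict with the protocol.** A reader might infer that the SAP contradicts addendum Section 10.3.1. It does not. That section says "baseline is Visit 3 assessment in Study CGAP unless otherwise specified" and leaves details to the SAP, Table CGAP. 5.4 specifies otherwise, and SAP 5.5 states that the SAP supersedes the protocol's statistical plans. SAP 5.5.4 is also open that baseline body weight is the last value before injection.
- **Baseline before washout.** A reader might infer that CM baseline weights generally precede withdrawal of preventives. Step 4 shows this is possible only for patients on preventives with a Visit 1 to Visit 2 interval of 30–45 days. It cannot occur at the 33-day end of the range.
- **A biased dose comparison.** CM patients are randomised 1:1, so drift has the same expected distribution in CM120 and CM240 and favours neither. The safety models make no between-arm comparison (SAP 5.5.1).
- **EM against CM.** A Visit 3 weight would not give the two populations a common reference. EM Visit 3 is the end of treatment in Study CGAN, when the LY/LY patients were already on galcanezumab.
- **Unscheduled weights.** Categorical safety analyses include unscheduled visits (SAP 5.5.12.1), so an unscheduled pre-dose weight could replace or join the screening value there. The MMRM ignores such values.
- **Size.** Every input in step 7 is assumed. It also uses one post-baseline value, whereas Table CGAP. 5.4 takes the minimum or maximum over Study Period III. Even the direction is open.
- **Timing.** SAP Version 3 followed the interim lock, by which all randomised patients had had the chance to reach Month 6 (SAP 5.5, 5.8.1). A new weighing cannot help them.

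All of this stands. It narrows the point to the absolute CM weight results and how they are labelled. It does not remove the missing measurement.

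**Conclusion.** The point holds in limited form. For CM patients without an unscheduled pre-dose weight, every baseline rule for the Study Period III and combined-period weight analyses returns the Visit 1 value, 33 to 90 days old at first dose. Change before dosing is therefore included in the absolute CM mean changes and the 7% gain and loss rates, for a measure listed under the primary objective.

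The 33–90 day range and the shares in step 5 follow from the documents' visit windows and nominal visit spacing. The bias in kilograms or percentage points does not: it depends on a drift the documents do not give, and the step 7 figures show sensitivity only. The documents do not support a claim that the CM120 against CM240 contrast is biased, or that baseline weights in general predate the stopping of preventives.

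**What to change.** In the CM Schedule of Activities, add a weight before the injection at Visit 3. In Table CGAP. 5.4, define the CM weight baseline for both the continuous and the categorical analyses as the Visit 3 weight, with Visit 1 used only if Visit 3 is missing. This closes the 33–90 day gap for any patient weighed at Visit 3. It costs one weighing at a visit that already includes vital signs, ECG and laboratory tests, plus one line in each document.

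For patients already dosed without a Visit 3 weight:
- footnote Table CGAP. 5.4 and each weight table that the CM baseline is the screening value, taken 33–90 days before the first dose;
- report the actual Visit 1 to Visit 3 gap by arm (CM120, CM240).

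This costs one footnote and one derived variable, and no planned analysis changes. By the stage of SAP Version 3, it is the only part that can still help patients already in the study.

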5.5.2. Patient Disposition

For disposition summary, treatment group is based on (EM120, EM240, CM120, CM240, LY_ALL)

The number and percentage of ITT patients who complete the study or discontinue early will be tabulated for the treatment groups for Study Period III and Study Period IV separately both overall and by visit. Reasons for discontinuation will be compared between treatment groups using Fisher's exact test for study period III with the ITT population. Descriptive statistics only will be presented for the treatment groups in Study Period IV with post-treatment population. Subcategories of discontinuation due to subject decision will be summarized too.

Listing of Subjects who discontinued for SP III or SP IV will be created for ITT population.

Patient allocation by investigator site will be summarized (the number of screened, randomized, discontinued from SP III, entered for SP IV, discontinued from SP IV) for all patients.

Summary of Reasons for Screen Failure will be created for all screen failure patients.

Listing of Detailed Reasons for Screen Failure will be created for all screen failure patients.

Listing of Patient population (e.g. PPS, safety population) by investigator will be created for all study periods for ITT population.

5.5.3. Important Protocol Deviations

For protocol deviation summary, treatment group is based on (EM120, EM240, CM120, CM240, LY_ALL)

Listings of subjects with important protocol deviations will be provided for ITT population. The following list of important protocol deviations will be determined before DBL. Detail criteria and methods will be specified in a separate document which also specify exclusion of PPS/ITT/safety population.

- Violation of informed consent :(e.g. Lack of informed consent or late informed consent)
- Serious Adverse event not reported
- Deviation related to inclusion/exclusion criteria
- Deviation of the rescreen criteria
- Deviation of the operation of Visit
- Deviation of the discontinuation criteria
- Deviation of study treatment dosing
- Deviation of concomitant drug and therapy
- Other important protocol deviations as determined by the Lilly clinical/medical group

Summary of important protocol deviations will be made for

- Baseline and SP III
- SP IV

Listing of Important Protocol Deviations (include flags whether affected to PPS/ITT/safety or not) will be made for

- Baseline and SP III
- SP IV

It is based on 4 arms (EM120, EM240, CM120, CM240).

